# 1.2 Study design

Figure 1 below presents the overall design of the study.

Study D1683C00005 is a 24-week, multi-center, randomised, parallel-group, double-blind, active-controlled Phase III study to evaluate safety and efficacy of therapy with saxagliptin 5mg co-administered with dapagliflozin 5mg added to metformin, compared to therapy with

Statistical Analysis Plan Amendment Study Code D1683C00005 Edition Number 4.0 Date 09th Aug 2017 saxagliptin 5mg or dapagliflozin 5mg added to metformin in adult patients with Type 2 Diabetes Mellitus (T2DM) who have inadequate glycaemic control (HbA1c  $\geq$ 7.5% to  $\leq$ 10.0%) on maximum tolerated dose (MTD) of  $\geq$ 1500mg/day of metformin monotherapy.

In this study, sites will be allowed to perform a pre-study screening assessment (at Week -3) prior to enrolment visit to screen for HbA1c criteria. All potentially eligible patients will be enrolled, provide informed consent, undergo screening for all applicable inclusion/exclusion criteria, and submit laboratory samples at Enrolment (Visit 1, 2 weeks prior to randomisation). Patients should be treated with a stable, MTD of metformin monotherapy ( $\geq$ 1500mg/day) for at least 8 weeks prior to enrolment, and remain on the same type and dose of metformin therapy for the duration of the study as the background therapy for all treatment arms as indicated below:

- 1. Dapagliflozin 5mg + saxagliptin 5mg + metformin
- 2. Dapagliflozin 5mg + saxagliptin placebo + metformin
- 3. Saxagliptin 5mg + dapagliflozin placebo + metformin

Study duration will be at least 27 weeks, including a 1-week pre-study Screening period, a 2-week enrolment period, and a 24-week double-blind treatment period.

#### **Figure 1 - Study Design**

## **1.3** Number of patients

Approximately 900 patients with T2DM with inadequate glycaemic control receiving metformin at a MTD of  $\geq$ 1500mg/day for at least 8 weeks prior to enrolment will be randomised to 1 of 3 treatment groups.

A sample size of 300 patients per group will provide at least 90% power to simultaneously detect a difference in mean change from baseline to week 24 in HbA1c of -0.30 (%) for both primary endpoint comparisons of saxagliptin plus dapagliflozin vs its components at the 2-sided -alpha = 0.05 level. This assumes a common standard deviation of 1.0% and a 3% non-evaluability rate.

## 2. ANALYSIS SETS

#### 2.1 Definition of analysis sets

There are four analysis (population) sets defined below for this study. Analysis sets will be finalized prior to unblinding of the study.

#### 2.1.1 Enrolled patients set

The enrolled patients set (EPS) will consist of all patients who sign informed consent. This data set will be used to summarize the patient disposition data.

#### 2.1.2 Full analysis set

The full analysis set (FAS) is defined as all randomised patients who take at least one dose of the study medication and have a baseline value for HbA1c. Analysis of the FAS will be based on the randomised treatment.

Note, that subjects from one site with potential serious GCP violations will be excluded from all tables and figures. A selection of key tables and figures will be rerun with the site data included to assess the impact of the exclusion. See section 2.2.

FAS will be used to summarize important PDs, patient demography and baseline data; and conduct efficacy analyses.

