#### 2.1.3 Per protocol set

The per protocol set (PPS) will be defined as all FAS patients without a relevant protocol deviation (PD) that might affect the primary analyses. The criteria for relevant protocol deviations are detailed in Section 2.2 below.

PPS will be used mainly to assess the sensitivity of the primary and secondary efficacy analyses conducted on FAS by excluding relevant PDs. Specifically, PPS will be used to summarize change of primary and secondary efficacy endpoints from baseline to week24, and repeat primary and secondary efficacy analyses done on FAS.

The safety analysis set (SAF) will be defined as all randomised patients who received at least one dose of study medication. This data set will be used to summarize safety data (AE, vital signs and laboratory parameters), and patient demography and their baseline data as well.

Note, that subjects from one site with potential serious GCP violations will be excluded from all tables and figures. A selection of key tables and figures will be rerun with the site data included to assess the impact of the exclusion. See section 2.2. If there is a difference between the SAF and FAS, baseline and demography data will also be presented for the FAS.

Data in this data set will be analysed based on randomised treatment, except in cases where a patient received a different treatment for the entire course of his/her participation in the double-blind treatment period. In this case, safety data for such a patient will be analysed based on the first treatment the patient actually received.

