| 11  | Randomized subjects who did not take the required study
medication (either saxagliptin, dapagliflozin or both) for
more than 2 consecutive weeks after randomization.   | Exclude data from PPS from the 15 th day onwards.   |

The Per protocol analysis will not be conducted if <10% of patients have relevant protocol deviations.

Note, during the conduct of the study, serious potential GCP violations were found in one site. These issues cast doubt on the validity of the data from this site. Consequently, all key tables and figures will include a version which excludes data from this site. Specifically, a selected set of key tables (which will include the primary and key secondary endpoints and key safety tables) will be run twice (both with and without the site) to assess the impact of this exclusion. Listings will include all sites.

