## 4.2 Analysis methods

#### 4.2.1 Patient disposition

A clear accounting of the disposition of all patients who enter the study will be provided, from screening to study completion. Summaries of patient disposition will be presented by treatment and overall (column), while summaries in the EPS (when applicable) will be presented only by overall (column). The following patient disposition summaries will be provided:

• Number and percentage of patients in the EPS, FAS, PP and SAF populations will be presented on their own as well as by country, study centre and overall (row) (Analysis Population: EPS).

- Number and percentage of screen-failure patients (i.e., patients enrolled but not randomized), further classified by reasons for screen failure (Analysis Population: EPS).
- Number and percentage of patients who complete the study and who withdraw from the study, further classified by reasons for withdrawal from the study (as recorded on Disposition (DS) page of Case Report Form [CRF]).(Analysis Population: FAS)

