## 5. INTERIM ANALYSES (NOT APPLICABLE)

#### 6. CHANGES OF ANALYSIS FROM PROTOCOL

The following updates were made 6th Oct 2016:

- include 6 weeks in the exploratory analysis of change from baseline in HbA1c
- include 6 weeks in the exploratory analysis of change from baseline in FPG
- include 6 weeks in the exploratory analysis of change from baseline in Body Weight
- include 6 weeks in the exploratory analysis of change from baseline in systolic BP
- include change from baseline in diastolic BP at 6, 12 and 24 weeks in the exploratory analysis The following updates were made 30th of July 2017:
- Subjects from one site with potential serious GCP violations will be excluded from all tables and figures. A selection of key tables and figures will be rerun with the site data included to assess the impact of the exclusion.

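### The one-site exclusion in the SAP reaches disposition, exposure and non-key safety tables, against the SAP's own set definitions, and section 2.2 words it differently from the other four places

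*SAP*

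**What the plan says.** SAP 2.1.2 (full analysis set) carries a note that "subjects from one site with potential serious GCP violations will be excluded from all tables and figures". The same note stands in the safety analysis set definition (numbered 2.1.4 in the SAP's table of contents) and in 4.1 (general principles), and 6 (changes from protocol) lists it as a change made on 30 July 2017. All four add the same qualification: "A selection of key tables and figures will be rerun with the site data included to assess the impact of the exclusion".

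Section 2.2, to which the first three of these places refer the reader, is worded differently: "all key tables and figures will include a version which excludes data from this site". It goes on to say that "a selected set of key tables (which will include the primary and key secondary endpoints and key safety tables) will be run twice", with and without the site, and that listings keep every site. The reason it gives is that potential serious GCP violations at the site put the validity of its data in question.

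The set definitions carry no site condition. The enrolled set is everyone who signs consent (2.1.1). The full analysis set is randomised, dosed patients with a baseline HbA1c (2.1.2). The safety set is "all randomised patients who received at least one dose of study medication". Section 4.2.1 opens with: "A clear accounting of the disposition of all patients who enter the study will be provided".

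**The concern.** Doubt about data validity can justify leaving a site out of an efficacy estimate. It does not change the fact that its patients consented, were randomised and took study drug. The definitions and the disposition section say that these patients are counted, and the note says that they are left out of the tables. A programmer cannot follow both.

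If the note is followed, the disposition table no longer adds up to the number randomised, and the breakdown by study centre lacks a centre. Safety tables outside the key group understate the number exposed and the number with events. Because listings keep every site, one report would hold tables and listings that do not reconcile. For example, a death at the site would be in the listing of deaths (4.2.5.2). It would be absent from the adverse event overview that counts deaths (4.2.5.1), unless that overview is among the tables rerun with the site.

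**Working it through.** No figure in the plan is in dispute, so the check sets the SAP sections side by side.

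**Step 1: scope of the exclusion.** The note in 4.1 is a general principle for the whole of section 4. It therefore reaches disposition (4.2.1), baseline (4.2.2), exposure and compliance (4.2.3), efficacy (4.2.4) and safety (4.2.5). No exception is written.

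**Step 2: what each output would contain.**

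| Output | SAP section | Set | Site in the base table? | With-site version assured? |
|---|---|---|---|---|
| Analysis-set counts (overall, by country, by centre), screen failures | 4.2.1 | Enrolled | No | No |
| Completion and withdrawal | 4.2.1 | Full analysis | No | No |
| Demography and baseline | 4.2.2 | Safety | No | No |
| Exposure, compliance | 4.2.3 | Safety | No | No |
| Primary and key secondary endpoints | 4.2.4 | Full analysis | No | Yes (2.2) |
| AE overview, SAE, AESI and hypoglycaemia tables | 4.2.5.1 | Safety | No | Only if chosen as key |
| Laboratory and vital sign tables | 4.2.5.3, 4.2.5.4 | Safety | No | Only if chosen as key |
| Listings of AEs, hypoglycaemic events and deaths | 4.2.5.1, 4.2.5.2 | All sites | Not a table; site kept | Not needed |

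Section 2.2 says that the selected set will include the primary, key secondary and key safety tables. It does not list the key safety tables and does not mention disposition or exposure. A with-site version of those may be made, but nothing in the SAP requires it.

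**Step 3: the mismatch.** Let N be the number randomised and s the number of these at the excluded site. The definitions and 4.2.1 lead to a disposition total of N. The note leads to N − s. Listings cover N. The gap between tables and listings is s patients and whatever events they had. The documents do not give s. For orientation only, the protocol synopsis plans about 900 patients at about 120 sites, an average of 900/120 = 7.5 patients, or 7.5/900 = 0.8%. The actual site may be far from the average.

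**Step 4: the wording of section 2.2.** In the four other places the site is out, and key outputs are rerun with it in. In 2.2 the first sentence says that key outputs will have a version without the site. Taken alone, that makes the with-site table the base and confines the exclusion to key outputs. The sentence after it gives the purpose of running tables twice as measuring the effect of the exclusion, which agrees with the other four places. So one sentence is out of step with the rest.

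**The case against.** The strongest reply is that the plan is open about the exclusion and largely covers it. The exclusion is declared in section 6, the reason is given in 2.2, and analysis sets are to be final before unblinding (2.1). Primary, key secondary and key safety tables exist both ways. All reported adverse events, hypoglycaemic events and deaths are listed for every site, and deaths are also described in narratives. All of this stands.

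Two stronger readings are tempting, and the documents do not support them.

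- A reader might infer that the site's events disappear from the report. They do not, because the listings keep every site and key safety tables have a with-site version. Nor can one say that most adverse event tables lose the site, since the key tables are not listed.
- A reader might infer that the confirmatory test is undefined. Four consistent statements make the without-site analysis the base, with a rerun to measure the effect of the exclusion. That is how a main analysis and its sensitivity analysis are related. The loose sentence in 2.2 does not outweigh them.

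It can also be argued that 4.2.1, as the specific rule for disposition, overrides the general note, especially as the enrolled set carries no site note of its own. That reading is possible. But 4.1 states no exception, and a programmer should not have to choose between the two.

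Finally, keeping doubtful data in the default safety tables is partly a matter of preference. This stands too, and it is why both versions are asked for rather than a with-site version alone.

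**Conclusion.** The point holds as one of scope and consistency. Followed as written, the SAP gives disposition, exposure and non-key safety tables that leave out randomised, dosed patients. These tables contradict the unchanged set definitions and 4.2.1, and they do not reconcile with the listings. Section 2.2 needs to be brought into line with 2.1.2, the safety set definition, 4.1 and 6.

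The conclusion rests on two readings. First, the general note in 4.1 covers disposition, which it reaches through its blanket wording without naming it. Second, some of the site's patients were randomised and dosed, which follows from the exclusion being written into the full analysis and safety sets.

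The number of patients and events affected is unknown, because the site's size is not given. The number of safety tables affected is unknown, because the key tables are not listed. Loss of power is not part of the point: a site near the planned average would hardly change it, and the documents give no basis for assuming a larger one. The change is worth making before unblinding, mainly for complete safety and disposition reporting.

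**What to change.** Make three changes to the SAP before unblinding.

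1. In 4.1 and 4.2.1, exempt disposition and analysis-set counts from the exclusion. Every randomised patient is then counted, and the excluded site's patients are shown on a line of their own.
2. In 2.2, list the tables produced both with and without the site. Besides the primary and key secondary endpoints, name exposure, the adverse event overview, SAEs, adverse events leading to discontinuation, and adverse events of special interest.
3. Reword 2.2 to match 2.1.2, the safety set definition, 4.1 and 6. State once that the without-site efficacy analysis is confirmatory and the with-site run is the sensitivity analysis.

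The cost is SAP wording and a few extra table runs. The downside is that some with-site safety tables will contain data of doubtful quality; a footnote on those tables can say so.

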#### 2.1.3 Per protocol set

The per protocol set (PPS) will be defined as all FAS patients without a relevant protocol deviation (PD) that might affect the primary analyses. The criteria for relevant protocol deviations are detailed in Section 2.2 below.

PPS will be used mainly to assess the sensitivity of the primary and secondary efficacy analyses conducted on FAS by excluding relevant PDs. Specifically, PPS will be used to summarize change of primary and secondary efficacy endpoints from baseline to week24, and repeat primary and secondary efficacy analyses done on FAS.

The safety analysis set (SAF) will be defined as all randomised patients who received at least one dose of study medication. This data set will be used to summarize safety data (AE, vital signs and laboratory parameters), and patient demography and their baseline data as well.

Note, that subjects from one site with potential serious GCP violations will be excluded from all tables and figures. A selection of key tables and figures will be rerun with the site data included to assess the impact of the exclusion. See section 2.2. If there is a difference between the SAF and FAS, baseline and demography data will also be presented for the FAS.

Data in this data set will be analysed based on randomised treatment, except in cases where a patient received a different treatment for the entire course of his/her participation in the double-blind treatment period. In this case, safety data for such a patient will be analysed based on the first treatment the patient actually received.

## 2.2 Violations and deviations

Important PDs are defined as those deviations from the protocol likely to have an impact on the efficacy and/or safety of study treatments. Protocol deviations that the study team considers to be important will be tabulated or listed in CSR. Relevant PDs are defined as those deviations likely to have an impact on the primary efficacy analysis and are the basis for exclusion of data for the per protocol analysis of the primary endpoint. The criteria for relevant protocol deviations and any action to be taken regarding the exclusion of patients or affected data from the per protocol primary efficacy analysis are defined in

## Table 1 – List of Important Protocol Deviations below.

Important and Relevant PDs will be identified from two sources:

- 1. IMPACT monitoring deviations will be reported as a protocol deviation in the IMPACT system by the Site Monitor. A report will be generated in IMPACT and will be sent from a study team representative to Biometrics & Information Sciences (B&I).
- 2. Statistical programming deviations will be identified by execution of programs run on the clinical database.

The reports or information collected from the IMPACT monitoring report will be reviewed and assessed periodically during study conduct by AZ/vendor study team and documented in an EXCEL spreadsheet (or other appropriate format).

The final derivation of the per protocol criteria will be done using both approaches above. A meeting of the study team will be held prior to unblinding to make the final determination (or rules for the final determination in the case of criteria which require unblinding) of all subject and data exclusions for the per protocol analysis based on consideration of the results of the 2 approaches above and resolving any inconsistencies between the two approaches. In the case of a discrepancy (e.g. statistical programming shows patient is 100% compliant with study drug but IMPACT monitoring report shows patient is non-compliant), the statistical

Note that the content of **Table 1** is not an exhaustive list of important PDs but rather applies only to relevant PDs for the per protocol analysis. A complete list of protocol deviations (including important protocol deviations) will be compiled separately and finalised prior to DBL.

#### Table 1 – List of Important Protocol Deviations

| No. | Deviation   | Action   |
|-----|---|--|
| 1   | Randomized subjects without Type II diabetes or with
central laboratory HbA1c at screening outside of
specified limits (i.e. violation of inclusion criterion # 2a
or screening HbA1c value out of range specified in 2a)  | Completely Exclude from PPS  |
| 2   | Randomized subjects who did not receive stable doses of
metformin for at least 8 weeks prior to enrolment (visit
1) (i.e. violation of inclusion criterion 2c)  | Completely Exclude from PPS  |
| 3   | Randomized subjects with abnormal free T4 values at
enrolment (i.e. violation of exclusion criterion #9c)  | Completely Exclude from PPS  |
| 4   | Randomized subjects with a history of
haemoglobinopathy with the exception of sickle cell trait
(SA) or thalassemia; or chronic recurrent hemolysis. (i.e.
violation of exclusion criterion #7a)   | Completely Exclude from PPS  |
| 5   | Randomized subjects with current or frequent use of
therapeutic doses of systemic glucocorticoids (i.e.
violation of exclusion criterion #8e) at enrolment  | Completely Exclude from PPS  |
| 6   | Patient's overall compliance is $< 80\%$ or $> 120\%$ .   | Completely Exclude from PPS  |
| 7   | Patient incorrectly received rescue medication  | Exclusion from the day the rescue medication was given onwards.  |
| 8   | Randomized subjects newly initiating or changing
treatment with systemic glucocorticoids for >= 5 days
after enrolment  | Exclude data from PPS from the 5 th day onwards. If this day is prior to randomization then this becomes a complete exclusion.  |
| 9   | Randomized subjects who used anti-hyperglycaemic
medication other than IP, metformin or rescue therapy
for more than 14 days during the 8 weeks prior to
enrolment (i.e. violation of exclusion criterion #8a) or
afterwards (i.e. use of prohibited concomitant diabetes
medication). | Exclude data from PPS from the 15 th day onwards. If this day is prior to randomization then this becomes a complete exclusion. |
| 10  | Randomized subjects who took no metformin or < 1500 mg metformin per day for more than 2 consecutive weeks after enrolment.   | Exclude data from PPS from the 15 th day onwards. If this day is prior to randomization then this becomes a complete exclusion. |
| 11  | Randomized subjects who did not take the required study
medication (either saxagliptin, dapagliflozin or both) for
more than 2 consecutive weeks after randomization.   | Exclude data from PPS from the 15 th day onwards.   |

The Per protocol analysis will not be conducted if <10% of patients have relevant protocol deviations.

Note, during the conduct of the study, serious potential GCP violations were found in one site. These issues cast doubt on the validity of the data from this site. Consequently, all key tables and figures will include a version which excludes data from this site. Specifically, a selected set of key tables (which will include the primary and key secondary endpoints and key safety tables) will be run twice (both with and without the site) to assess the impact of this exclusion. Listings will include all sites.

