# 7.2 Dose and treatment regimens

The study consists of an Enrolment visit (Visit 1), a Randomisation visit (Visit 2), followed by a 24-week randomised, double-blind, double-dummy treatment period.

AstraZeneca or a designated representative will provide all IPs. In the event the patient loses her/his study medication, the study center should notify the Investigator immediately in order to receive a replacement kit via the IVRS/IWRS.

At Visit 2, patients will be randomly assigned to 1 of the 3 treatment arms and randomised study medication will be dispensed in kits as dapagliflozin 5mg tablets, saxagliptin 5mg tablets, and matching placebo tablets. Study medication will be dispensed according to the schedule presented in Table 1.

During the treatment period, patients will take 2 tablets everyday: 1 from the dapagliflozin/placebo bottle, 1 from the saxagliptin/placebo bottle.

The first doses of study medication will be taken at the study site. Patients will subsequently self-administer saxagliptin, dapagliflozin, and matching placebos QD orally for the 24-week treatment period.

On days of scheduled study visits, patients should bring their study medication with them to the study site and will take that daily dose as directed by study site personnel.

If any dose is missed, it should be taken as soon as noticed, unless it is almost time for the next dose, in which case patients should skip the missed dose and take the medicine at the next regularly scheduled time.

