#### 4.2.3.3 Measurement of Treatment Compliance

Percent treatment compliance is calculated during treatment period for study medication (i.e. saxagliptin or matching placebo and dapagliflozin or matching placebo) and overall.

(Number of tablets taken / Planned number of tablets)\*100%

Where the planned number of tablets is calculated as:

(End date – Start date +1) \* prescribed daily number of tablets

The number of tablets taken is calculated as:

total number of tablets dispensed - total number of tablets returned

based on the CRF accountability pages.

Overall compliance is defined as :

(Total number of tablets taken / Total planned number of tablets)\*100; where

the planned number of tablets is calculated as:

(latest end date – earliest start date +1) \* prescribed daily number of tablets

and the number of tablets taken is calculated as:

total number of tablets dispensed - total number of tablets returned.

A patient is considered compliant if percent compliance is  $\ge 80\%$  and  $\le 120\%$ . For each type of medication and overall, the number and percent of patients compliant during the treatment period will be displayed for the SAF.

For metformin, a summary for the SAF, including number and percentage of subjects that ever took metformin therapy at a dose of <1500mg per day during the treatment period, will be provided separately in addition to the compliance summary of the study medications.

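### SAP Table 1, row 6, tests compliance pooled over both bottles, so a patient who intermittently takes only about 60% of one component can stay in the per-protocol set

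*SAP*

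**What the plan says.** - **SAP Table 1, row 6.** The criterion is that the patient's "overall compliance is" below 80% or above 120%. The action is complete exclusion from the PPS.
- **SAP 4.2.3.3, overall compliance.** It is one ratio, "Total number of tablets taken / Total planned number of tablets", times 100. The planned number is the span "latest end date – earliest start date +1" multiplied by the prescribed daily tablets.
- **Protocol 7.2.** During treatment "patients will take 2 tablets everyday: 1 from the dapagliflozin/placebo bottle, 1 from the saxagliptin/placebo bottle". The daily number in the overall formula must therefore be 2.
- **SAP 4.2.3.3, limits.** "A patient is considered compliant if percent compliance is" at least 80% and at most 120%, so exactly 80% passes. Protocol 7.6 gives the same limits without saying whether they apply per bottle or pooled.
- **SAP 4.2.3.3, per medication.** Compliance is also calculated for saxagliptin or its placebo and for dapagliflozin or its placebo, with a plain start and end date. "For each type of medication and overall, the number and percent of patients compliant during the treatment period will be displayed" for the safety set. These values do not enter row 6.
- **SAP Table 1, row 11.** If either component, or both, is not taken for more than 2 consecutive weeks, data are dropped from the 15th day onwards.
- **SAP 2.1.3 and 2.2.** The PPS serves as a sensitivity check on the full analysis set (FAS). The PP analysis is not run if fewer than 10% of patients have relevant deviations.

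**The concern.** The primary objective is superiority of the combination over each agent alone, so what matters in a PP analysis is whether each component was taken. A pooled tablet count cannot show that, because full use of one bottle offsets poor use of the other.

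The consequence depends on the arm:

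- **Combination arm.** A patient short of saxagliptin resembles a dapagliflozin-arm patient, and the reverse. Keeping such patients pulls the PP contrast with the other component toward zero.
- **One-drug arms.** One bottle is placebo. A patient short of the active drug can be lifted to 80% by placebo tablets. An under-dosed comparator makes the combination look better, not worse.

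SAP 2.2 defines relevant deviations as those likely to affect the primary efficacy analysis. Missing 40% of an active component plausibly fits that definition, and row 11 shows that the SAP already regards adherence to each component as relevant. Row 6 patients also count toward the 10% condition, so the wording of row 6 could affect whether the PP analysis is run.

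**Working it through.** The plan gives no worked compliance figure. Its one calculated figure, power of at least 90%, does not bear on this point, and it reproduces: 300 × 0.97 = 291 evaluable per arm gives 95.1% per comparison, and 0.9514² = 90.5% for both if they are treated as independent.

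**Inputs.** 24 weeks = 168 days; 1 tablet per bottle per day (Protocol 7.2), so 168 planned per bottle and 336 in total; limits 80% and 120% inclusive (SAP 4.2.3.3).

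**Formula.** Overall % = 100 × (tablets from bottle A + tablets from bottle B) / 336.

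**Step 1: what row 6 lets through.**

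| Bottle A | Bottle B | Overall | Row 6 |
|---|---|---|---|
| 60% (100.8) | 100% (168) | 268.8/336 = 80.0% | stays in |
| 101 tablets | 168 | 269/336 = 80.06% | stays in |
| 100 tablets | 168 | 268/336 = 79.76% | excluded |
| 50% (84) | 100% (168) | 252/336 = 75.0% | excluded |

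With bottle B at 100%, the floor for bottle A is 160 − 100 = 60%. At the upper limit, 140% with 100% pools to 120% and stays in.

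**Step 2: the same rule in a one-drug arm.** Active 60% with placebo 100% gives 80.0% and stays in. Active 100% with placebo 50% gives 75.0% and is excluded completely. The rule can keep the under-dosed patient and drop the fully dosed one.

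**Step 3: does row 11 catch the patient?** Taking 101 of 168 tablets means 67 missed doses. I placed 67 missed doses at random over 168 days for 100,000 simulated patients. A run of more than 14 days occurred in about 0.002%, and the median longest run was 5 days. Real missed doses cluster more than this, but moderate clustering also escapes: four separate gaps of 14 days and one of 11 make 4 × 14 + 11 = 67, with no gap over 2 weeks. If all 67 fall in one block, row 11 applies and data from the 15th day of the gap are dropped.

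**Step 4: what a per-medication limit would do.** I read the plain start and end dates in the per-medication formula as that medication's own dates.

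- The intermittent patient scores 60% on one medication and would be excluded.
- A patient who stops one bottle for good after day 101 scores 101/101 = 100% on that medication and 80.06% overall, so only row 11 acts.
- On a common period instead (earliest start to latest end), a patient who stops one bottle after day 120 scores 120/168 = 71.4% on it and would be excluded completely. Today that patient has (120 + 168)/336 = 85.7% overall and loses only the later data under row 11.

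**The case against.** The best defence is that row 6 does not stand alone.

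- **Row 11 is component-specific.** This stands. A reader might infer that PP adherence is judged only on the pooled figure; the documents do not support that. What remains uncovered is intermittent under-dosing without a gap of more than 2 weeks.
- **Other sources feed the decision.** SAP 2.2 also uses monitor-reported deviations, and a team meeting before unblinding makes the final determination. Protocol 7.6 requires a patient interview, a tablet count and recorded dates of missed doses. The SAP sentence on resolving conflicts between the two sources breaks off in the text available to me, so I cannot say that the pooled figure always prevails. Still, Table 1 gives that meeting no per-drug percentage to apply.
- **Divergence between bottles may be rare.** This is plausible, since the patient takes one tablet from each blinded bottle every day. The documents give no rate. Patterns such as 110% with 50% or 120% with 40% also pool to 80%, but a reader should not take them as expected. They imply either use that Protocol 6.5 defines and records as overdose, or unreturned tablets.
- **Per-medication compliance is displayed.** A reader of the report would see how many patients in each arm fall outside the limits for each drug. That shows the extent of the problem but does not remove those patients from the PP estimate.

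A reader might also infer that under-dosing always dilutes the treatment effect. It does not: in the one-drug arms the bias runs in favour of the combination, so the net direction is not known in advance.

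**Conclusion.** The point holds as a narrow gap in the PPS definition. With full use of the other bottle, intermittent intake of one component can fall to about 60% (101 of 168 tablets) without triggering row 6 or, usually, row 11.

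This rests on three assumptions: the overall formula pools both bottles at two tablets a day, treatment lasts the full 168 days, and missed doses form no gap of more than 2 weeks.

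The effect on HbA1c cannot be sized from the documents. It would need the number of such patients per arm and the response to partial dosing, and neither is given.

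The consequence is small. Only the conditional PP sensitivity analysis is touched. A reader might infer a threat to the primary result; the documents do not support that, because the primary analysis uses the FAS and applies no compliance exclusion. This is a worthwhile clarification, not a flaw in the main analysis.

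**What to change.** Change the row 6 criterion to: *compliance with either study medication, or overall compliance, is <80% or >120%*, using the per-medication compliance already defined in SAP 4.2.3.3, with each medication's own start and end dates.

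Add one sentence stating that permanent stopping of one component is handled by row 11 (data excluded from the 15th day onwards) and not by complete exclusion under row 6. The sentence also settles an existing overlap: a patient who stops one bottle after day 100 or earlier already falls below 80% overall (268/336 = 79.76%) and is excluded completely, although row 11 alone would keep the early data.

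A common period for the per-medication limits would be a poor choice. It needs a new derivation and, as in step 4, would turn row 11's partial exclusion into a complete one.

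**Cost.** Two lines of SAP text and little programming. The rule can be applied blind and identically in all arms. The PPS would probably be slightly smaller, by a number the documents do not give. It would also lose some one-drug-arm patients for missed placebo alone: 100% active with 70% placebo is 85% overall and stays in today, but would be excluded. The pooled rule already does this in part, as the 100% with 50% case shows.
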